### **Summary of AEs Onset after the Last Study Dose**

For subjects who either complete or are early terminated the study, incidence of hyperactivity-related AEs will be summarized by analysis group. [Attachment 4.5.5](#) provides the definition of hyperactivity-related AEs per preferred term and lower level term. These terms were originally defined in Appendix 2 of SN-0434 and were communicated with the Psychiatry Division of FDA on Oct 24, 2014.

### **Subjects continued from Study D1050326**

#### **Treatment-Emergent Mania:**

Treatment-emergent mania is defined as a YMRS score of  $\geq 20$  on any 2 consecutive OL visits (ie, including OL baseline visit for subjects who were randomized to lurasidone group in the core study or excluding the visit(s) with study day  $\leq$  Day 1 for subjects randomized to placebo group) or at the final assessment in OL treatment period, or any TEAE of mania or hypomania.

Frequency and percentage of subjects experiencing treatment-emergent mania in the first 52-week treatment period and during the overall open-label treatment period will be presented by analysis subgroup, respectively.

In addition, frequency and percentage of subjects of following categories will be presented for the first 52-week treatment period and the overall open-label treatment period, accordingly.

- YMRS score of  $\geq 20$  on any 2 consecutive OL visits or at the final assessment
- YMRS score of  $\geq 16$  on any 2 consecutive OL visits or at the final assessment
- YMRS score of  $\geq 15$  on any 2 consecutive OL visits or at the final assessment
- Any TEAE of mania or hypomania
- Any TEAE of mania or hypomania or YMRS score of  $\geq 16$  on any 2 consecutive OL visits or at the final assessment
- Any TEAE of mania or hypomania or YMRS score of  $\geq 15$  on any 2 consecutive OL visits or at the final assessment

## 2.6.5. Laboratory Measurements

Laboratory data will be summarized for each laboratory test listed in [Attachment 4.3](#).

Descriptive statistics (N, mean, standard deviation, median, and range) will be reported by analysis group and analysis subgroup for each continuous laboratory analyte at the DB baseline, OL baseline, each post-OL baseline visit, W52 endpoint, and endpoint for absolute value as well as changes from DB baseline and OL baseline, respectively. Categorical results (eg, urinalysis tests) will be summarized at DB baseline, OL baseline, each post-OL baseline visit, W52 endpoint, and endpoint by analysis group using frequency and percentage. All lab values will be presented in the data listings.

Per a notice from lab vendor of the study, the test agent or assay for Estradiol was switched from Estradiol II to Estradiol III during the mid-course of the study. Lab Specification Document (LSD) was updated on Sep 01, 2015 to add normal reference range for Estradiol III. Due to this change, Estradiol data are presented under 2 test names (ie, 'Estradiol II' and 'Estradiol III') in the raw lab dataset. It should be noted that for three completed core studies (D1050325, D1050301, D1050326), only Estradiol II was used and reported in the raw lab dataset; 'Estradiol II' in raw data was mapped as 'Estradiol' in the lab analysis dataset of the core studies. In the lab analysis dataset of study D1050302, all data under test name of 'Estradiol', 'Estradiol II', or 'Estradiol III' will be mapped to 'Estradiol (overall)'; Estradiol results under different test agents will be kept as is (ie, mapped as 'Estradiol II', and 'Estradiol III', respectively). In summary output, results for 'Estradiol (overall)', 'Estradiol II', and 'Estradiol III' will be presented, separately.

Prolactin values will be summarized by analysis group and gender (male, female, and overall). Results for glucose, insulin, and lipid tests (HDL cholesterol, LDL cholesterol, total cholesterol, and triglycerides), along with a derived variable for homeostasis model assessment of insulin resistance (HOMA-IR), will be presented separately by fasting status, which includes fasting only, and overall (fasting, non-fasting, or unknown). HOMA-IR will be derived based on glucose and insulin results as follows:

HOMA-IR = Glucose (mg/dL) x Insulin (mU/L) / 405 for conventional unit;

HOMA-IR = Glucose (mmol/L) x Insulin (μU/L) /22.5 for SI unit.

The normal reference ranges for laboratory tests will be used to determine whether the laboratory test value is below, within, or above the normal range. Shifts from DB baseline and shifts from OL baseline over time will be produced by analysis group to show the percentage of subjects with laboratory test values below, within, and above the normal range.

Potentially Markedly Abnormal Laboratory Values (PMALV) per conventional unit and the equivalent International System of Units (SI) for selected laboratory parameters can be found in Table 3.1. The criterion of PMALV is satisfied if a value falls into the potentially markedly abnormal range. The number and percentage of subjects with treatment emergent PMALV in the first 52-weeks treatment period and during overall treatment period, and the number and percentage of subjects who meet the threshold in [Table 3.2](#) per conventional unit and the equivalent International System of Units (SI) by study visit will be presented by analysis group and by analysis subgroup as needed.

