#### 2.1.5. Definition of Baseline Assessments

The following definitions will be used for effectiveness and safety assessments unless otherwise specified:

- **DB Baseline** (ie, Baseline assessment of the double-blind studies [D1050301, D1050325, or D1050326]): the last assessment made on or before the 1st dose of double-blind study medication as described in the SAPs of the core studies;
- **OL Baseline** (ie, Endpoint assessment of the double-blind studies [D1050301, D1050325, or D1050326] or Baseline assessment of the open-label study [D1050302]): the last assessment made on or before Day 1 of the extension study.

According to the protocol, measurement collected at OL Baseline is same as the value at visit 9 (ie, Week 6) (Study 301/325) or visit 8 (ie, Week 6) (study 326). For operation convenience, the protocol specified that data collected at the EOT visit of the core studies were to be recorded in core studies only and were not to be saved in the clinical database RAVE of the extension study. OL Baseline data in the Study Data Tabulation Model (SDTM) datasets of the study D1050302 will be obtained from corresponding core studies directly.

Unless otherwise specified, at each study visit of study D1050302, data derivation rule and missing imputation method for aggregated parameter that involves multiple individual items (eg, total score, subscale score, or composite score), are same as the corresponding ones in individual core study SAP. DB Baseline is defined same as the Baseline in individual core study per core study SAPs. DB Baseline used in the analysis of study D1050302 will be extracted from corresponding Analysis Data Set (ADS) of the core studies directly unless otherwise specified.

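### Change from baseline in 'Estradiol (overall)' subtracts an assay II baseline from assay III follow-up at every visit after the laboratory's switch, so the reported change includes an unknown assay offset

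*SAP*

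**What the plan says.** SAP 2.6.5 (Laboratory Measurements) discloses that "the test agent or assay for Estradiol was switched from Estradiol II to Estradiol III during the mid-course of the study". It adds that the laboratory specification was updated on 1 September 2015 with a reference range for assay III, and that "for three completed core studies (D1050325, D1050301, D1050326), only Estradiol II was used and reported in the raw lab dataset". In the core analysis datasets the assay II results carry the plain name 'Estradiol'.

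For the extension, results under all three names are mapped to a parameter called 'Estradiol (overall)', and the assay-specific results are also kept. The outputs follow that structure: "results for 'Estradiol (overall)', 'Estradiol II', and 'Estradiol III' will be presented, separately".

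The same section summarises each continuous analyte "for absolute value as well as changes from DB baseline and OL baseline, respectively", at each visit, at the Week 52 endpoint and at endpoint. It does not exempt estradiol.

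SAP 2.1.5 fixes where the baselines come from. For the open-label baseline, "OL Baseline data in the Study Data Tabulation Model (SDTM) datasets of the study D1050302 will be obtained from corresponding core studies directly". For the double-blind baseline, "DB Baseline used in the analysis of study D1050302 will be extracted from corresponding Analysis Data Set (ADS) of the core studies directly".

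**The concern.** A change score is interpretable when both measurements are on the same scale. Here the baseline is always assay II, while follow-up is assay II before the switch and assay III after it. Neither document gives a conversion factor, bridging data, a same-assay rule or a caveat on the pooled change.

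Hormonal parameters are a listed safety variable (Protocol 6.1 and 14.4.2) in a two-year study of subjects who entered the core studies at 6 to 17 years (SAP 1). A drift in mean estradiol could be read as a drug effect or as maturation when part of it is the laboratory's change of assay. The reverse could also happen: an offset could hide a real shift.

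**Working it through.** The plan states no estradiol figure, so there is none to reproduce. The check traces the derivation rule and then shows what it does to a mean.

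**Step 1. Assay on each side of the subtraction**

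| Quantity | Source | Assay |
|---|---|---|
| DB baseline | core analysis datasets (SAP 2.1.5) | II |
| OL baseline | core studies (SAP 2.1.5) | II |
| Extension value before the switch | SAP 2.6.5 | II |
| Extension value after the switch | SAP 2.6.5 | III |

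In 'Estradiol (overall)' the change is therefore II minus II before the switch and III minus II after it.

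**Step 2. Effect on a visit mean**

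Write each assay III result as the value assay II would have given plus an offset. Then

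reported mean change = mean change had all samples been on assay II + f × b,

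where f is the share of that visit's samples on assay III and b is the mean III-minus-II offset in those samples. The error is zero only if f = 0 or b = 0.

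The documents do not give b. Assuming a range of -20% to +20% of the baseline mean, for illustration only, f × b in percent of the baseline mean is:

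| f | b = -20% | -10% | 0 | +10% | +20% |
|---|---|---|---|---|---|
| 0 | 0 | 0 | 0 | 0 | 0 |
| 0.25 | -5 | -2.5 | 0 | 2.5 | 5 |
| 0.5 | -10 | -5 | 0 | 5 | 10 |
| 0.75 | -15 | -7.5 | 0 | 7.5 | 15 |
| 1 | -20 | -10 | 0 | 10 | 20 |

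**Step 3. Does f vary?**

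Hormones are drawn at Weeks 12, 28, 52, 76 and 104 (Protocol 11.4), with target days 85, 197, 365, 533 and 729 (SAP Table 2). The switch date is not stated. Taking 1 September 2015 as a stand-in, a visit falls on or after it if the first dose was on or after 1 September 2015 minus (target day - 1):

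- Week 12 (84 days back): 9 June 2015
- Week 28 (196 days): 17 February 2015
- Week 52 (364 days): 2 September 2014
- Week 76 (532 days): 18 March 2014
- Week 104 (728 days): 3 September 2013

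The later the visit, the earlier a subject could have entered and still be on assay III, so f is likely to rise with visit week. It is also likely to differ by core study. Entry from D1050325 ended by its lock on 16 December 2014, so its Week 28 target day falls by 30 June 2015 at the latest, before the stand-in date. Entry from D1050301 and D1050326 could run to 10 February 2016 and 12 October 2016. These are upper bounds on entry, so the share for any cohort cannot be derived.

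The Endpoint and Week 52 Endpoint rows take the last available value (SAP 2.1.6), so there the assay depends on when each subject's last sample was drawn.

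**Step 4. Do the assay-specific outputs supply the missing change?**

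- Estradiol II: the change is same-assay, but exists only for pre-switch visits. It also needs the core results named 'Estradiol' to serve as its baseline, which the SAP does not spell out.
- Estradiol III: there is no assay III baseline, so there is no same-assay change.

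For post-switch visits the only change with a defined baseline is the pooled one.

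**The case against.** The strongest reply is that the SAP already does much of what is needed. It discloses the switch, keeps the assays apart as well as pooling them, plans observed values by visit, and plans shifts below, within and above the normal range, for which an assay III range was added. This stands in part. A reader might infer that no planned table removes the assay effect; that goes too far, because the Estradiol II output does so for pre-switch visits, and range shifts are less exposed if each assay's own range is applied. The SAP does not say which range the pooled parameter uses. Nor is separating drug effect from maturation something any assay rule could achieve in an uncontrolled extension.

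A reader might also infer that most D1050326 follow-up is cross-assay, because that core study ran on assay II until about October 2016 while the assay III range dates from September 2015. The documents do not support this. The September date is a specification update, and assay II was evidently still in use for D1050326 core samples about 13 months later. The switch was either study-specific or later, and the SAP does not say which. A false change expressed in concentration units would likewise rest on no document input: neither a baseline mean nor an offset is given, and the documents do not say that the two assays disagree.

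The impact is narrow. Estradiol is measured in females only, at five scheduled draws. Primary safety is adverse events, serious adverse events and discontinuations (Protocol 14.4.1), and no hypothesis is tested. Estradiol appears in neither the markedly-abnormal criteria nor the threshold table in SAP 2.6.5, so no flag depends on the pooled change. This stands, and limits the weight of the point.

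Finally, the schizophrenia CSR is already complete (SAP 1), so a changed rule would make it differ from the full CSR for D1050301. That calls for a note. It is not a reason to keep the rule, since lock 2 and the full CSR were still ahead when the SAP was written.

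**Conclusion.** The point holds as a structural defect: on the SAP's own rules, every post-switch change in 'Estradiol (overall)' is assay III minus assay II, and the separate tables do not replace it. This needs only that some follow-up was measured on assay III, which the SAP states.

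The error in a visit mean is f × b. Its size and direction are unknown, because b and the switch date are not in the documents; the ±10% at f = 0.5 rests on an assumed offset of ±20% and is illustration only. That f rises with visit week and differs by core-study group is likely, not established.

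It should be corrected before the full CSR, but it touches one analyte, in females, in a descriptive secondary safety output, and leaves the primary safety analysis alone.

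**What to change.** In SAP 2.6.5:

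1. Report estradiol change from DB and OL baseline only for same-assay (II to II) pairs, and state that the core-study parameter 'Estradiol' is the baseline for Estradiol II.
2. Do not report change for 'Estradiol (overall)' across assays.
3. For assay III, report observed values and below, within or above status against the assay III reference range.
4. Footnote the switch in the estradiol tables, and note in the full CSR how it affects the estradiol change results in the completed schizophrenia CSR.

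The cost is a few lines of SAP text, one programming condition and the note on the earlier CSR. The real downside is information: fewer subjects contribute to estradiol change, and later visits will have little or none. A post-switch change could be reported only with a documented II-to-III conversion or bridging data, and the documents contain neither.

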**Table 1.1 Criteria for Potentially Markedly Abnormal Laboratory Values for Pediatric and Adolescent Subjects**

Conventional Unit		SI Unit	
Parameter (Unit)	Potentially Markedly Abnormal Range	Parameter (Unit)	Potentially Markedly Abnormal Range
Hematology			
Hemoglobin (g/dL)	Female: $\leq 9.5$ , Male: $\leq 11.5$ Female or Male: $\geq 17.2$	Hemoglobin (g/L)	Female: $\leq 95$ , Male: $\leq 115$ Female or Male: $\geq 172$
Haematocrit (fraction, %)	$\leq 30, \geq 50$	Haematocrit (V/V)	$\leq 0.3, \geq 0.5$
WBC ( $10^3/\mu\text{L}$ )	$\leq 2.8, \geq 16$	WBC ( $10^9/\text{L}$ )	$\leq 2.8, \geq 16$
RBC ( $10^6/\mu\text{L}$ )	$\leq 3.0, \geq 6.0$	RBC ( $10^{12}/\text{L}$ )	$\leq 3.0, \geq 6.0$
Platelet Count ( $10^3/\mu\text{L}$ )	$\leq 100, \geq 500$	Platelet Count ( $10^9/\text{L}$ )	$\leq 100, \geq 500$
Eosinophils (%)	$\geq 10$	Eosinophils (%)	$\geq 10$
Neutrophils (%)	$\leq 15$	Neutrophils (%)	$\leq 15$
Clinical Chemistry			
ALP (U/L)	$\geq 3 \times \text{ULN}$	ALP (U/L)	$\geq 3 \times \text{ULN}$
ALT (U/L)	$\geq 2 \times \text{ULN}$	ALT (U/L)	$\geq 2 \times \text{ULN}$
AST (U/L)	$\geq 2 \times \text{ULN}$	AST (U/L)	$\geq 2 \times \text{ULN}$
Total Bilirubin (mg/dL)	$\geq 2.0$	Total Bilirubin (umol/L)	$\geq 34.2$
Albumin (g/dL)	$< 50\% \text{ LLN}$	Albumin (g/L)	$< 50\% \text{ LLN}$
Creatinine (mg/dL)	$\geq 2.0$	Creatinine (umol/L)	$\geq 176.8$
Creatine Phosphokinase (CPK) (U/L)	$\geq 450$	Creatine Phosphokinase (CPK) (U/L)	$\geq 450$
LDH (U/L)	$\geq 3 \times \text{ULN}$	LDH (U/L)	$\geq 3 \times \text{ULN}$
GGT (U/L)	$\geq 150$	GGT (U/L)	$\geq 150$
Sodium (mEq/L)	$\leq 130, \geq 150$	Sodium (mmol/L)	$\leq 130, \geq 150$
Potassium (mEq/L)	$\leq 3, \geq 5.5$	Potassium (mmol/L)	$\leq 3, \geq 5.5$
Bicarbonate (mEq/L)	$< 18, > 30$	Bicarbonate (mmol/L)	$< 18, > 30$
Calcium (mg/dL)	$< 8.4, > 11.5$	Calcium (mmol/L)	$< 2.1, > 2.875$
Chloride (mEq/L)	$< 90, > 115$	Chloride (mmol/L)	$< 90, > 115$
Blood Urea Nitrogen (mg/dL)	$\geq 30$	Blood Urea Nitrogen (mmol/L)	$\geq 11.25$

Glucose (fasting) (mg/dL) (random) (mg/dL)	$\leq 45, \geq 126$ $\leq 45, > 200$	Glucose (fasting) (mmol/L) (random) (mmol/L)	$\leq 2.4975, \geq 6.993$ $\leq 2.4975, > 11.1$
Prolactin (ng/mL)	$\geq 1 \times \text{ULN}$	Prolactin (mIU/L)	$\geq 1 \times \text{ULN}$
Lipid Panel (Fasting)			
Total Cholesterol (mg/dL)	$\geq 240$	Total Cholesterol (mmol/L)	$\geq 6.216$

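### Two SI-unit laboratory rules in the SAP do not match their conventional-unit partners: the HOMA-IR formula (1000-fold) and the blood urea nitrogen limit (5%)

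*SAP*

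**What the plan says.** SAP section 2.6.5 (Laboratory Measurements) adds HOMA-IR as a derived variable, reported with glucose, insulin and lipids by fasting status. It gives one formula per unit system:

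- Conventional: "HOMA-IR = Glucose (mg/dL) x Insulin (mU/L) / 405 for conventional unit".
- SI: "HOMA-IR = Glucose (mmol/L) x Insulin (μU/L) /22.5 for SI unit".

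The same section introduces the abnormality limits as "Potentially Markedly Abnormal Laboratory Values (PMALV) per conventional unit and the equivalent International System of Units (SI) for selected laboratory parameters", so the two columns of the table are meant to express the same limits. The table is cited in the text as Table 3.1 but captioned Table 1.1. Its row "Blood Urea Nitrogen (mg/dL") has a limit of at least 30, and the paired entry "Blood Urea Nitrogen (mmol/L") has a limit of at least 11.25.

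No other section of the SAP or protocol corrects either item.

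**The concern.** HOMA-IR is one index, and its value should not depend on the unit system in which glucose is recorded. The SI line changes the insulin unit from mU/L to μU/L, although the change of constant already accounts for the whole change in the glucose unit. In the abnormality table, the urea nitrogen pair implies a conversion factor that does not follow from the composition of urea, while the neighbouring rows convert correctly.

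Both items feed safety reporting in children and adolescents, in a study whose primary objective includes long-term safety. HOMA-IR is a metabolic measure, and its SI values would be unusable if programmed as written. The urea nitrogen limit decides who is counted as having a potentially markedly abnormal value, so the count could depend on the column used. SI output is a realistic need: two of the three core studies recruited worldwide, and the schizophrenia report was prepared for submission to the European agency (SAP section 1).

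**Working it through.** **1. HOMA-IR**

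Inputs from the SAP are the constants 405 and 22.5 (section 2.6.5) and the glucose conversion implied by the abnormality table: 6.993/126 = 2.4975/45 = 0.0555 mmol/L per mg/dL. In addition, 1 mU/L = 1000 μU/L.

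The constants: 405/22.5 = 18, and 405 x 0.0555 = 22.48, which is 22.5 to within 0.1%. The move from 405 to 22.5 is therefore exactly the glucose conversion and leaves nothing for insulin.

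| Glucose, insulin | Conventional | SI as written (insulin in μU/L) | SI with insulin in mU/L |
|---|---|---|---|
| 90 mg/dL, 10 mU/L | 90 x 10/405 = 2.222 | 4.995 x 10,000/22.5 = 2220 | 4.995 x 10/22.5 = 2.220 |
| 126 mg/dL, 20 mU/L | 126 x 20/405 = 6.222 | 6.993 x 20,000/22.5 = 6216 | 6.993 x 20/22.5 = 6.216 |

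The ratio of the SI formula as written to the conventional one is 999 in both rows, that is, 1000 apart from the 0.1% rounding in 22.5. With mU/L the ratio is 0.999.

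**2. Blood urea nitrogen**

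Inputs from the SAP are 30 mg/dL and 11.25 mmol/L, an implied factor of 11.25/30 = 0.375. The check also needs the mass of nitrogen in one mole of urea (two atoms, 28.0134 g). The documents do not give this; it is taken from basic chemistry.

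- Forward: 30 mg/dL = 300 mg/L, and 300/28.0134 = 10.709 mmol/L (factor 0.357).
- Backward: 11.25 x 2.80134 = 31.515 mg/dL.
- Difference: 11.25/10.709 = 1.0505, so the SI limit is 5% too high for equivalence.

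Other readings do not recover 11.25 either: a factor rounded to 0.36 gives 10.80, treating the 30 mg/dL as whole urea (60.056 g/mol) gives 5.00, and counting a single nitrogen atom gives 21.42.

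**3. Control: the other converted limits**

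The same calculation was applied to other pairs in this table and to the lipid thresholds in Table 3.2, again with standard molar masses.

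| Analyte | Factor implied by the SAP | Deviation from the molar-mass value |
|---|---|---|
| Total bilirubin | 34.2/2 = 17.1 | -0.02% |
| Creatinine | 176.8/2 = 88.4 | 0.00% |
| Calcium | 2.1/8.4 = 2.875/11.5 = 0.25 | 0.2% |
| Glucose | 0.0555 | -0.01% |
| Total, HDL and LDL cholesterol | 6.216/240 = 1.036/40 = 4.144/160 = 0.0259 | 0.14% |
| Triglycerides | 1.921/170 = 2.26/200 = 0.0113 | 0.05% |
| Blood urea nitrogen | 11.25/30 = 0.375 | 5.05% |

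Urea nitrogen is the only outlier. The factor 0.375 looks like 0.357 with two digits exchanged, but that is a guess about its origin and the conclusion does not need it.

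**The case against.** On HOMA-IR, the slip is in a unit label; the constant 22.5 is right. The line above shows insulin in mU/L, nothing in the documents says that insulin is recorded in or converted to μU/L, and a programmer who used mU/L or μU/mL would obtain correct values. A result of 2220 in place of 2.22 would also be hard to miss. HOMA-IR is not named in the protocol and has no abnormality limit.

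On urea nitrogen, the affected band is only about 1.5 mg/dL wide, and the documents give no distribution from which to say how many subjects fall in it. The SAP states the limits in both unit systems but does not clearly say that the abnormality counts will be produced in both. In the reporting sentence, the reference to both units attaches to Table 3.2, which has no urea nitrogen row. The documents also do not show which of the two limits was intended. Finally, two interim analyses and the schizophrenia report are already done, so a correction is not entirely free.

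These points limit the practical effect and they stand. They do not remove either mismatch. The SAP is the specification from which programs are written and checked, and it should not need to be disregarded to give the right answer. If the flag is derived only once, the SAP still has to say which limit applies.

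**Conclusion.** Both rules are wrong as written. The SI formula for HOMA-IR is inconsistent with the conventional one by a factor of 1000. This follows from the SAP's own figures and the definition of the milli- and micro-prefixes. The SI limit for urea nitrogen is 5% above the stated equivalent (11.25 against 10.71 mmol/L). This rests on the mass of nitrogen in urea, which the documents do not state.

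The harm is conditional. HOMA-IR output is affected only if the stated insulin unit is followed literally. The urea nitrogen flag is affected only for values from 30 to just under 31.5 mg/dL, and only if the SI limit is used. The correction is nevertheless worth making, because both items determine reported safety results.

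**What to change.** - **HOMA-IR.** In the SI formula, give insulin in mU/L (equal to μU/mL) and keep 22.5. If the laboratory reports insulin in pmol/L, state the conversion to mU/L as a separate first step.
- **Blood urea nitrogen.** Reconcile the pair and state which limit governs. The cleanest route is to derive the abnormality flag once in conventional units and carry it over to the SI display. If 30 mg/dL is the intended limit, the SI entry becomes 10.71 mmol/L. Comparing converted values with that rounded figure should be avoided, because exactly 30 mg/dL converts to 10.709 and would fail a limit of at least 10.71. Deriving the flag once avoids this.
- **Completed outputs.** Check whether the programs for the two interim analyses and the schizophrenia report followed the SI rules as printed. If so, record the correction in the full study report.

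The cost is two edits to the SAP, the matching program lines and the check of completed outputs. According to SAP section 1, the second database lock and the full report are still to come, so the text can be corrected before they are produced.

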**Table 3.2 Thresholds for Selected Laboratory Parameters**

Conventional Unit		SI Unit	
Parameter (Unit)	Threshold	Parameter (Unit)	Threshold
Prolactin (ng/mL)	$\geq 1 \times \text{ULN}$	Prolactin (mIU/L)	$\geq 1 \times \text{ULN}$
	$\geq 2 \times \text{ULN}$		$\geq 2 \times \text{ULN}$
	$\geq 3 \times \text{ULN}$		$\geq 3 \times \text{ULN}$
	$\geq 5 \times \text{ULN}$		$\geq 5 \times \text{ULN}$
HDL-C (mg/dL)	$\leq 30$	HDL-C (mmol/L)	$\leq 0.777$
	$\leq 40$		$\leq 1.036$
LDL-C (mg/dL)	$\geq 160$	LDL-C (mmol/L)	$\geq 4.144$
	$\geq 200$		$\geq 5.180$
Total Cholesterol (mg/dL)	$\geq 200$	Total Cholesterol (mmol/L)	$\geq 5.180$
	$\geq 240$		$\geq 6.216$

A listing of subject data for those who have experienced at least once PMALV in the open-label study will be generated.

Urine drug screen results will be presented for each parameter at DB baseline, OL baseline, post-OL baseline visit, W52 endpoint, and endpoint. Number and percentage of positive and negative results will be displayed by analysis group.

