## 4.3. Clinical Laboratory Tests

Blood Chemistry Tests
aspartate aminotransferase
alanine aminotransferase
albumin
alkaline phosphatase
bicarbonate
blood urea nitrogen
calcium
chloride
creatinine
gamma-glutamyl transferase
phosphorous

potassium	
sodium	
total bilirubin a	
total protein	
lactate dehydrogenase	
fasting (non-random) triglycerides	
fasting (non-random) serum cholesterol	
fasting (non-random) serum high-density lipoprotein cholesterol	
fasting (non-random) serum low-density lipoprotein cholesterol	
fasting glucose	
prolactin	
whole blood hemoglobin A1c	
creatine phosphokinase	
Endocrine Tests	
free thyroxine test	
thyroid-stimulating hormone test	
Hormonal Parameters	
follicle stimulating hormone (female subjects only)	
luteinizing hormone (female subjects only)	
testosterone (male subjects only)	
estradiol (female subjects only)	
serum human chorionic gonadotropin ( $\beta$ -hCG) (female subjects $\geq$ 11 years of age only)	
urine human chorionic gonadotropin ( $\beta$ -hCG) (female subjects $\geq$ 11 years of age only)	
Hematology Tests	
white blood cell count	
white blood cell differential	
eosinophilic leukocyte count	
basophilic leukocyte count	
neutrophil count	
lymphocyte count	
monocyte count	
platelet count	
hemoglobin	
blood hematocrit	
red blood cell count	
red cell distribution width	
red blood cell indices:	
mean corpuscular volume	
mean corpuscular hemoglobin concentration	
mean corpuscular hemoglobin	
Urinalysis Tests	
color	
appearance	
total ketones	
urobilinogen	
bilirubin	
red blood cells	
leukocyte esterase	
nitrite	
pH	
protein	
specific gravity	

glucose
microscopic evaluation b
Urine Drug Screen
amphetamines
benzodiazepines
barbiturates
cocaine
tetrahydrocannabinol
ethanol
methadone
methamphetamine
opiates
phencyclidine

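### The markedly abnormal laboratory table (SAP Table 3.1) screens neutrophils and eosinophils by percentage only, so its any-visit counts can put subjects in the wrong order of absolute count (minor)

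*SAP*

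**What the plan says.** SAP section 2.6.5 applies a simple rule: "The criterion of PMALV is satisfied if a value falls into the potentially markedly abnormal range". The ranges are in Table 3.1, which is headed Table 1.1 where it is printed. In its hematology block, WBC (2.8 or less, 16 or more, x10^3/µL), RBC and platelets are in absolute units. Neutrophils (15 or less) and eosinophils (10 or more) are in percent in both the conventional and the SI column. Table 3.2, "Thresholds for Selected Laboratory Parameters", covers prolactin and cholesterol fractions and has no hematology row.

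The panel in SAP Attachment 4.3, as in Protocol Appendix A, lists "neutrophil count" and "eosinophilic leukocyte count" as well as the WBC differential.

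The role of PMALV is set elsewhere in the SAP. Section 2.1.3 drops additional visits within a window from the by-visit summaries and relies on PMALV and the worst-case analyses to bring those measurements in. Section 2.1.7 names PMALV among the worst-case analyses. Section 2.6.5 reports it for the first 52 weeks and for the whole treatment period.

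The absolute counts are also covered by other displays in section 2.6.5: descriptive statistics including the range at each visit, Week 52 endpoint and endpoint; normal-range shifts ("Shifts from DB baseline and shifts from OL baseline over time will be produced by analysis group"); and listings of all laboratory values. Just below Table 3.2 the SAP adds: "A listing of subject data for those who have experienced at least once PMALV in the open-label study will be generated".

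**The concern.** A percentage of white cells corresponds to different absolute counts at different WBC values. A limit of 15% is a low count when WBC is low and a much higher one when WBC is high. A table that screens on the percentage alone can therefore leave a lower count unflagged and flag a higher one. For eosinophils the same fault runs in the other direction.

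This matters because PMALV is the laboratory display meant to gather every on-treatment value, including off-schedule repeats, into one count of subjects. The primary objective includes long-term safety in pediatric subjects over 104 weeks. A zero or small number in the neutrophil row could be read as a statement about absolute neutrophil counts, which the criterion does not measure.

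**Working it through.** The plan states no figure on this point, so there is nothing to reproduce. The check applies the Table 3.1 rules to pairs of values.

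**Inputs (SAP Table 3.1).** WBC is flagged at 2.8 or less, or 16 or more. Neutrophils are flagged at 15% or less. Eosinophils are flagged at 10% or more.

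**Formula.** Absolute count = WBC x percent / 100, in x10^9/L (the same number as x10^3/µL).

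| Cell | WBC | Percent | Count | WBC row | Percent row |
|---|---|---|---|---|---|
| Neutrophils | 3.0 | 16 | 0.48 | not met | not met |
| Neutrophils | 12 | 15 | 1.80 | not met | met |
| Neutrophils | 6.0 | 30 | 1.80 | not met | not met |
| Neutrophils | 6.0 | 16 | 0.96 | not met | not met |
| Neutrophils | 4.0 | 24 | 0.96 | not met | not met |
| Eosinophils | 3.0 | 10 | 0.30 | not met | met |
| Eosinophils | 15 | 9.9 | 1.49 | not met | not met |

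**Limits of the neutrophil gap.**
- An unflagged value needs WBC above 2.8 and neutrophils above 15%, so its count exceeds 2.8 x 0.15 = 0.42. Any count at or below 0.42 meets at least one row.
- The neutrophil row on its own, with WBC below 16, can flag counts up to just under 16 x 0.15 = 2.4. Between 0.42 and 2.4 (ratio 2.4 / 0.42 = 5.7), whether that row flags a given count depends on WBC.
- Unflagged counts below 0.5 lie between 0.42 and 0.50. They need WBC below 0.5 / 0.15 = 3.33 and neutrophils below 0.5 / 2.8 = 17.9%.
- A count of 1.80 meets the neutrophil row only at WBC of 1.80 / 0.15 = 12 or more.
- If 1.0 is taken as the cut-off, a count below it can go unflagged at any WBC above 2.8 and below 1.0 / 0.15 = 6.67.

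**Limits of the eosinophil gap.** An unflagged value needs WBC below 16 and eosinophils below 10%, so its count is below 16 x 0.10 = 1.6. With WBC above 2.8, the eosinophil row alone can flag counts down to just above 2.8 x 0.10 = 0.28. Between 0.28 and 1.6, whether that row flags a given count depends on WBC.

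**The case against.** The best defence is that this is a screening table for selected parameters and not the only place a low count would show.

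- The floor at 0.42 means that the WBC and percentage rows together already catch the lowest neutrophil counts.
- Blood is drawn at five scheduled extension visits (Protocol Table 9). The by-visit range shows the minimum count at each, so a value of 0.48 at a summarised visit would be printed.
- Protocol section 13.2 has the investigator judge every out-of-range value, repeat those that are possibly drug-related or of uncertain causality, and record clinically significant findings as adverse events. SAP section 2.6.4 tabulates treatment-emergent events over the whole period.
- No absolute cut-off appears in the documents, and hematology is not among the adverse events of special interest.

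Most of this stands, and it limits the point. A reader might infer that the plan generally fails to detect counts below 0.5, or that a severe case would be invisible in the report. The documents support neither: the unflagged band below 0.5 is 0.42 to 0.50, and the other displays cover the same data. Nor is a count of 1.80 flagged as a rule, as WBC 6.0 with 30% shows.

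The other displays do not supply a subject-level, any-visit count by depth. Shift tables separate only below, within and above normal. By-visit ranges omit additional values within a window, which is where a repeat test may fall. Adverse-event counts depend on the investigator's judgement. The dedicated listing contains only subjects who meet a PMALV criterion.

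**Conclusion.** The point holds as a minor weakness in a descriptive safety table. The PMALV analysis can flag a subject with a higher neutrophil count and pass over one with a lower count, and it can do the reverse for eosinophils. The missing output is the number of subjects with a markedly low neutrophil or markedly high eosinophil absolute count at any visit, together with their entry in the PMALV listing. No primary safety variable is affected.

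The misordering follows from Table 3.1 alone and needs no outside cut-off. The figures tied to 0.5 and 1.0 are illustrations that assume those cut-offs. The documents give no neutrophil or eosinophil reference range, so no count here is called normal or severe. They also give no distribution of WBC or of the differential, so the number of subjects affected cannot be estimated. The listed neutrophil and eosinophil tests are taken to be absolute counts. If they are not, WBC times the differential percentage gives the same quantity.

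**What to change.** Add absolute neutrophil and absolute eosinophil rows to SAP Table 3.1, using the collected counts or WBC times percent. The sponsor's medical review should set the reporting cut-offs and record them in the SAP before final database lock 2. Tabulate the rows for the first 52 weeks and for the whole treatment period, as for the other PMALV rows, and let them feed the PMALV listing. Keep the percentage rows for continuity with the core studies.

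The cost is a few table rows and their program; no new data are needed. The drawback is comparability. The new rows have no counterpart in the core-study outputs. SAP section 1 also says that final lock 1 has occurred and that the report for the schizophrenia subjects (271 enrolled from D1050301) is complete. Unless those outputs are rerun, the rows should be labelled in the full final report as added after lock 1.
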